2.2 Objectives

2.2.1 Primary objectives

Part A: To assess the safety and tolerability of single ascending oral doses of BEN8744 in healthy subjects

Part B: To characterise the effect of food on the pharmacokinetic (PK) profile of at least 1 oral dose of BEN8744

Part C: To assess the safety and tolerability of multiple ascending oral doses of BEN8744 in healthy subjects

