2.4 Type of trial

This is a Phase 1, single-centre trial to assess the safety, tolerability, PK and food effect of BEN8744 in healthy volunteers.

This trial will be in 3 parts, as follows:

Part A will test single doses of BEN8744 in a double-blind, randomised, placebo-controlled and dose-escalating design.

Part B will test the effect of food on the PK of BEN8744 in an open-label, randomised, 2-way crossover design.

Part C will test repeated doses of BEN8744 (once or twice daily for 14 days) in a double-blind, randomised, placebo-controlled and dose-escalating design.

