2.6.1 Part A

Part A will test single oral doses of BEN8744 in a double-blind, randomised, placebo-controlled and dose-escalating design.

Up to 5 groups of 8 subjects will be enrolled in Part A (Groups A1–A5). Each subject will have 1 study session, in which they will receive a single dose of BEN8744 or placebo, by mouth in the fasted state. The planned dose levels are: 2 mg (Group A1), 6 mg (Group A2), 20 mg (Group A3), 60 mg (Group A4), and 100 mg (Group A5). Additional intermediate or higher dose levels may be explored in 3 optional groups (Groups A6–A8), as detailed in section 8.5.2. At each dose level, 6 subjects will receive BEN8744 and 2 will receive matching placebo.

The dose will be escalated only if the safety and tolerability of the previous highest dose are acceptable, and the plasma concentrations of BEN8744 are predicted to remain below the exposure limit, as determined by the Safety Review Group (SRG). A dose level may be repeated or decreased, as required, based on emerging results.

Each new ascending dose will be staggered, such that 2 sentinel subjects will be dosed first, and randomised such that 1 subject receives BEN8744 and the other receives placebo. The remaining 6 subjects will be dosed at least 23 h later, at intervals of at least 10 min. If the planned dose escalation is changed such that a selected dose is no higher than a dose previously shown to cause no safety concerns, then sentinel subjects will not be required.

Subjects will be resident on the ward from 1 day before their dose (Day –1) until up to 72 h after dosing (Day 4). They will return for a follow-up visit 7 (± 2) days after their inpatient stay (Day 11 ± 2 days).

2.6.2 **Part B**

Part B will test the effect of food on the PK of BEN8744 in an open-label, randomised, two-way crossover design.

Up to 2 groups of 6 subjects will be enrolled in Part B (Groups B1 and B2). Each subject will have 2 study sessions, in which they will receive at least 1 dose of BEN8744, by mouth after either an overnight fast in one session or a high-fat breakfast in the other session. A subject's doses will be separated by a washout of at least 7 days (or 5 half-lives as determined in Part A, whichever is longer).

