8.1.2 Part B

Enrolment of up to 12 healthy subjects is planned, in up to 2 groups (Groups B1 and B2).

Each subject in Part B will have 2 study sessions (Sessions 1 and 2), in which they will receive a single dose of BEN8744, by mouth. Each subject will receive BEN8744 after an overnight fast of at least 10 h in one session, and after an FDA high-fat breakfast (1,013 kcal, 59.2 g fat [of which 28.1 g saturated fat]) in the other session; the order will be randomised 1:1, as shown in Table 7. A subject's doses

will be separated by a washout of at least 7 days (or 5 half-lives as determined in Part A, whichever is longer). Subjects dosed on the same day may be dosed at intervals of at least 10 min.

Table 7 Treatment sequence for each group (n=6 each) in Part B

	Session 1	Session 2
n=3 subjects	Fed	Fasted
n=3 subjects	Fasted	Fed

The dose to be tested in Group B1 will be decided following review of the interim safety, tolerability, and PK data from at least 3 dose levels in Part A, as described in section 8.5.3.

To reduce the risk of unexpectedly high plasma concentrations, the dose selected for Group B1 will be no higher than 50% of the highest dose tested in Part A that caused no safety concerns.

Group B2 is optional and may be required if the Sponsor decides to test the effect of food at an additional dose level (for example, if absorption and hence exposure is not proportional to dose in Part A) or under different conditions (eg with different fasting requirements or after a different meal such as a standard breakfast). The dose and food requirements for Group B2 will be decided following review of the interim safety, tolerability, and PK data from Group B1 and all available data from Part A.

Subjects will be screened within 28 days before their first dose of trial medication. Subjects will be resident on ward from 1 day before their dose (Day -1) until up to 72 h after dosing (Day 4). They will return for a follow-up visit 7 (± 2) days after their inpatient stay in Session 2 (Day 11 ± 2 days).

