Subjects who meet the above criteria will be considered discontinued from dosing. However, the investigator may ask the subject to continue their participation in the study, so they can be monitored for safety and PK, or the investigator may withdraw the subject from the trial.

9.4.3 *Replacement of withdrawn subjects*

Withdrawn subjects will be replaced at the discretion of the sponsor and investigator. Subjects withdrawn because of AEs considered possibly related to study treatment (see section 14.2) will not be replaced. Replacements for other withdrawn subjects will receive the treatments intended for the withdrawn subject, from the start of the trial. For subjects in Part B, the sponsor and investigator will decide which sessions the replacement subject will complete.

10 *Treatments*

10.1 *Treatments administered*

In Part A, subjects will receive a single oral dose of BEN8744 or placebo.

In Part B, subjects will receive a single oral dose of BEN8744 on 2 different occasions, separated by a washout of at least 7 days.

In Part C, subjects will receive once or twice-daily oral doses of BEN8744 or placebo for 14 days.

Fasting requirements are described in section 11.

All treatments will be administered orally with approximately 240 mL of water. All treatments will be given in the fasted state in Parts A, and in the fasted or fed state in Part C.

10.2 *Overdose*

Symptoms of overdose of BEN8744 are not yet known. In the case of accidental overdose, subjects should be treated symptomatically as no specific antidote is available.

10.3 *Blinding (Parts A and C only)*

The trial medication will be repackaged and relabelled by the HMR Pharmacy, according to the randomisation schedule. Active and placebo treatments will be labelled such that it is not possible to distinguish between them. If the expiry dates of placebo and active treatment differ, both treatments will be labelled with an expiry

date no later than the earlier of the 2 expiry dates. Each subject's treatment will be given a unique code number, traceable to the batch number of the medication.

The placebo and active treatments for each group will be identical in appearance, and similar in taste and smell. To maintain the blind nature of the trial, the same number of capsules will be given to each subject in a group.

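### Section 9.4.3 allows a Part B replacement to complete only one session, which adds no within-subject fed:fasted contrast to a six-subject crossover

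*Combined protocol and SAP*

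**What the plan says.** Section 2.2.1 gives Part B's primary objective: "To characterise the effect of food on the pharmacokinetic (PK) profile of at least 1 oral dose of BEN8744". Section 2.4 gives the design: "Part B will test the effect of food on the PK of BEN8744 in an open-label, randomised, 2-way crossover design". Section 8.1.2 says "Each subject in Part B will have 2 study sessions", one fasted and one after a high-fat breakfast. Table 7 puts three subjects of each group of six in each sequence.

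Section 9.4.3 makes replacement discretionary and contains three further rules:

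- Exclusion: "Subjects withdrawn because of AEs considered possibly related to study treatment (see section 14.2) will not be replaced".
- General rule: "Replacements for other withdrawn subjects will receive the treatments intended for the withdrawn subject, from the start of the trial".
- Part B: "For subjects in Part B, the sponsor and investigator will decide which sessions the replacement subject will complete".

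The Part B sentence gives no criterion, no timing and no requirement that both sessions be completed. Section 10.5 gives a replacement its own number, that of the withdrawn subject plus 100.

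On analysis, the PK parameter population in section 16.2.3 takes any subject with derivable parameters and does not require both sessions. The food-effect ANOVA in section 16.2.7 names formulation as its only term and judges the 90% CI of fed:fasted against 80–125%. Section 16.2.1 leaves a separate analysis plan to be written before database lock.

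**The concern.** A crossover estimates the food effect from each person's own fed and fasted values, so stable differences between people cancel. Suppose subject 2003 is dosed fed in Session 1 and leaves, and subject 2103 is dosed only in the fasted session. The group then has six fed and six fasted values but only five people with both. The sixth fed and fasted values belong to different people, and section 6.2.4 describes between-subject variation as high.

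With six subjects per group, each contrast is one-sixth of the evidence on a primary objective. Part B also feeds the decision whether Part C is dosed fed or fasted (sections 8.1.3 and 8.5.4). A replacement exists to recover what the withdrawal cost, and a one-session replacement means dosing another volunteer without recovering it.

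**Working it through.** **The plan's own figures.** Two groups of 6 make 12, which agrees with section 9.1. Section 16.3 gives no formal sample size, so there is no power or precision figure to reproduce.

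**Inputs.**

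- AUCinf at 60 mg, n = 6: range 494–2,390 (Table 2), ratio 4.84.
- AUCinf at 20 mg, n = 6: range 77.30–210 (Table 2), ratio 2.72.
- Expected range of six normal values: 2.534 SD.
- Within-subject CV: not in the documents; assumed 15–40%.

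**Total log-SD (sT) = ln(max/min)/2.534.**

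- 60 mg: ln(4.84)/2.534 = 0.622
- 20 mg: ln(2.72)/2.534 = 0.394

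These are rough, since each rests on the extremes of six people. At 60 mg, values from two different people differ with log-SD 0.622 × √2 = 0.88, a factor of about 2.4 at 1 SD, with no food effect at all.

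**Within-subject log-SD (sw) = √ln(1 + CV²).** This gives 0.149, 0.198, 0.294 and 0.385 at CV 15, 20, 30 and 40%.

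**True standard error of the log fed:fasted ratio.**

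- Six true pairs: sw√(2/6)
- Five pairs, incomplete one left out: sw√(2/5)
- Five true pairs plus one composed of two people: √[(5·2sw² + 2sT²)/36]

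| Assumed CV | 6 pairs | 5 pairs | Mixed, 60 mg | Rise | Mixed, 20 mg | Rise |
|---|---|---|---|---|---|---|
| 15% | 0.086 | 0.094 | 0.166 | 93% | 0.122 | 41% |
| 20% | 0.114 | 0.125 | 0.180 | 57% | 0.140 | 22% |
| 30% | 0.169 | 0.186 | 0.213 | 26% | 0.180 | 6% |
| 40% | 0.222 | 0.244 | 0.250 | 13% | 0.223 | 0% |

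Rises are against six true pairs, from unrounded values. With the 60 mg spread, leaving out the incomplete pair beats mixing two people at every CV shown. With the 20 mg spread that holds only at 15% and 20%.

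**Subject fitted as a fixed effect.** Each one-session person is absorbed by their own subject term, so five contrasts remain. The standard error rises by √(6/5) = 1.095. The degrees of freedom of the two-period analysis fall from 4 to 3, so t goes from 2.132 to 2.353, and the 90% CI is 1.095 × 2.353/2.132 = 1.21 times as wide on the log scale. The one-session replacement recovers none of this.

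**Bias or precision?** In a simulation with no food effect (100,000 runs, sT = 0.62, CV 20%, mixed pair treated as a true pair), coverage of the 90% CI was 90% with six true pairs and 92% with one mixed. The median CI factor went from ×/÷1.25 to ×/÷1.37. The chance of the CI lying inside 80–125% fell from 19% to 8%.

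**The ANOVA as written.** With formulation as the only term, the standard error is computed as sT√(2/6) on 10 degrees of freedom. At 60 mg that is 0.622 × 0.577 = 0.359. Multiplied by t = 1.812 it gives 0.651, a CI of about ×/÷1.9. Simulated medians were 1.83–1.85, with or without a one-session replacement.

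**The case against.** The sentence permits a one-session replacement; it does not direct one, and completing both sessions is among the choices. Harm needs a chain: withdrawal between sessions, not for a possibly related adverse event, then a decision to replace, then a decision for one session. That is right, and it limits the point to one contrast of six.

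Nor do the documents pair two people. Separate numbering under section 10.5 keeps the records distinct, so the mixed-pair column shows what could happen without a rule, not a prescribed analysis. The analysis plan could still set that rule. It could not, however, create a within-subject contrast that was never collected.

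The strongest objection is that the model in section 16.2.7 ignores pairing even if nobody withdraws, so changing section 9.4.3 alone leaves the reported CI essentially where it was. This stands. It is the larger weakness, and the fix must cover it. It does not dispose of the point, because under a corrected model the one-session replacement still restores nothing.

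Three stronger readings are tempting and not supported:

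- **Biased food effect.** A reader might infer that differences between people would be systematically counted as food effect. If the choice of sessions is unrelated to results, they add noise of either sign, and simulated coverage is not degraded.
- **One mismatched pair decides the outcome.** At 60 mg the geometric mean ratio could move by 4.84^(1/6) = 1.30 for AUCinf, or (688/130)^(1/6) = 1.32 for Cmax. That requires the highest and lowest of six people to form the pair; at 20 mg the same extreme is 2.72^(1/6) = 1.18. The plan judges the 90% CI, not the point ratio. Group B1 is also capped at half the highest Part A dose without safety concerns: at most 30 mg if that dose is 60 mg, 50 mg if 100 mg, 70 mg if 140 mg.
- **Results-driven choice.** Part B is open-label and the rule has no timing, but nothing says Session 1 concentrations inform who is replaced or for which session.

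**Conclusion.** The point holds in limited form, as a cheap improvement. Section 9.4.3 allows a one-session replacement that cannot contribute to the comparison Part B is designed to make, and nothing elsewhere in the documents withdraws that permission. When the rule is used this way, one of six contrasts is lost. If the half-records are compared across people, precision worsens by an amount that depends strongly on dose and within-subject variability, from negligible to nearly double the standard error. If they are not, the group is left with five contrasts despite the replacement.

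This rests on log-SDs taken from the range of six subjects at each of two Part A doses, on an assumed within-subject CV, and on a choice of sessions unrelated to results. The Group B1 dose is not fixed in the documents, so the 20 mg and 60 mg figures are illustrations, not predictions.

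**What to change.** In section 9.4.3, replace the Part B sentence with: *A Part B replacement will complete both sessions, in the sequence assigned to the withdrawn subject.* Add that a withdrawn subject's single session is listed and described but not paired with another subject's session.

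In section 16.2.7, include subject in the food-effect model, with sequence and period. Without that, the change to section 9.4.3 does not reach the reported 90% CI.

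The cost is a short text change in each section and, for each subject actually replaced, at most one extra session with its dose, residence and blood samples. Planned numbers do not change, since section 9.1 already excludes replacements, and the Part B blood volume in Table 15 already covers two sessions.

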10.4 Unblinding procedure

If unblinding is required in the interest of the safety of a subject (for example, in a medical emergency), the principal investigator or delegate will open the individual code-break envelope for that subject without prior consultation with the sponsor. In that event, the principal investigator or delegate will notify the sponsor as soon as possible (within 24 h) that the randomisation code has been broken for the subject. If unblinding may be helpful, but is not required immediately (for example, the information may be useful to make decisions for other subjects in the group), wherever possible, an investigator will discuss the matter with the sponsor before opening any individual code-break envelopes.

When the trial database for the relevant part has been locked, the HMR statistician will inform the sponsor of his or her intention to break the randomisation code. The statistician will break the code, and do the statistical analysis of the relevant data.

10.5 Method of assigning subjects to treatment groups

After passing all of the screening assessments, subjects will be allocated to study part and group, according to their availability and the scheduled trial dates.

Subjects will be numbered consecutively, in the order in which they arrive on the ward and are entered into the trial. Subject numbers are presented in Table 8. Subject numbers will be allocated to treatments (active or placebo) according to a randomisation schedule prepared by an independent HMR statistician, using a SAS program.

Sentinel subject numbers in Part A are provided in Table 8; at each new dose level, 1 sentinel subject will receive active treatment and 1 sentinel subject will receive placebo.

Randomisation is described further in section Table 8.

Table 8: Subject and sentinel numbers

	Group	Subject numbers	Sentinel subjects
Part A	A1	1001–1008	1001 and 1002
	A2	1009–1016	1009 and 1010
	A3	1017–1024	1017 and 1018
	A4	1025–1032	1025 and 1026
	A5	1033–1040	1033 and 1034
	A6 (optional)	1041–1048	1041 and 1042
	A7 (optional)	1049–1056	1049 and 1050
	A8 (optional)	1057–1064	1057 and 1058
Part B	B1	2001–2006	Not applicable
	B2 (optional)	2007–2012	Not applicable
Part C	C1	3001–3008	Not applicable
	C2	3009–3016	Not applicable
	C3	3017–3024	Not applicable
	C4 (optional)	3025–3032	Not applicable

Replacements for withdrawn subjects will be given a number equal to that of the subject that they replaced plus 100. So, Subject 1001 would be replaced by Subject 1101, and Subject 3017 would be replaced by Subject 3117, and so on.

10.6 Selection and timing of dose for each subject

The treatments to be administered and intervals between subjects are described in sections 8.1 and 10.1. Subjects will be randomly assigned to treatment, as described in section 10.5 above.

Because BEN8744 has never been given to humans before, in Part A each new ascending dose will be staggered as described in section 10.5.

In Part C, doses will be given at the same time each day (if once daily dosing) or every 12 h at the same time each day (if twice daily dosing). Doses will be given ± 15 mins from times on Day 1.

10.7 Previous and concomitant treatment

Previous treatment restrictions are described in section 9.3.

During the trial, concomitant medication may be given if the Investigator believes it to be necessary. In addition, up to 2 g paracetamol (acetaminophen) will be allowed per day for mild analgesia (up to 1 g per dose). Any other concomitant treatment

will be given only if deemed strictly necessary by the investigator or co-investigator. In any case, all concomitant treatments will be reported in the CRF along with their daily dosage, duration, and reasons for administration. Subjects who have received any concomitant treatment may be withdrawn from the trial at the discretion of an investigator.

10.8 Assessment of compliance

Subjects will be dosed on the research ward under the supervision of 2 suitably trained members of HMR staff. Mouth checks will be done immediately after dosing.

11 Dietary and lifestyle restrictions

Subjects will abide by HMR house rules while on the ward.

Part A

In Part A, subjects will fast (no food or drink other than water) overnight for at least 10 h before dosing, until 4 h after dosing. Standard meals and drinks will be provided at about 4, 10 and 24 h after dosing. Water will not be allowed for 1 h before and after dosing.

Part B

In Part B, subjects will receive a dose of trial medication in the fed and fasted states. The dose level, fasting requirements and whether the dose will be taken after a high-fat or standard breakfast will be decided by the SRG based on emerging data.

Group B1

- In one treatment session, subjects will fast (no food or drink other than water) overnight for at least 10 h before dosing, until 4 h afterwards, and water will not be allowed for 1 h before and after dosing.
- In the other treatment session, subjects will take their dose of BEN8744 after a standard high-fat breakfast consisting of: 2 fried eggs, 2 strips of bacon, 2 slices of toast and butter, 4 ounces of hash brown potatoes, and a glass of whole milk. Subjects will fast (no food or drink other than water) overnight and will start the breakfast approximately 30 min before dosing, and they must eat all of the breakfast at least 10 min before dosing.
- In both treatment sessions, standard meals and drinks will be provided at 4, 10 and 24 h after dosing. The content of those meals will be the same in both sessions.

Group B2

- In one treatment session, subjects will fast (no food or drink other than water) overnight for at least 10 h before dosing, until 4 h afterwards, and water will not be allowed for 1 h before and after dosing.
- In the other treatment session, subjects will take at least 1 dose of BEN8744 after a high-fat breakfast or a standard breakfast (consisting of 2 slices of toast, 1 bowl of cereal with semi-skimmed milk, 2 portions of butter/margarine, and 1 portion of jam) having fasted overnight. The dose level, dosing regimen, and the predose meal will be decided following review of the data from Group B1 and available data from Part A.
- In both treatment sessions, standard meals and drinks will be provided at 4, 10, and 24 h after dosing. The content of those meals will be the same in both sessions.

Part C

In Part C, we anticipate that doses will be given once or twice daily in the fasted state unless emerging data indicate they should be taken in the fed state. Fasting requirements in Part C will be decided by the SRG after review of results from Parts A and B. Therefore, for the morning dose, subjects will either:

- fast from midnight on the evening before each dose, until 4 h after their morning dose, on the first and last dosing days, and until 2 h after dosing on all other dosing days. Water will not be allowed for 1 h before and after dosing; or
- fast from midnight before each dose, until about 30 min before the morning dose on all dosing days. Subject will be given a standard breakfast to finish before dosing, consisting of 2 slices of toast, 1 bowl of cereal with semi-skimmed milk, 2 portions of butter/margarine, and 1 portion of jam. Water will not be allowed for 1 h before and after dosing.

In once-daily dosing sessions, standard meals and drinks will be provided at about 4 and 10 h after dosing on all dosing days, and at 24 h after the last dose on the final dosing day.

If subjects are dosed twice daily, they will take their evening doses approximately 1 h after dinner. Water will not be allowed for 1 h before and after dosing.

All parts

No food or drink containing cranberry, pomegranate, starfruit, grapefruit, pomelos, exotic citrus fruits or Seville oranges (including marmalade and juices made from these fruits) will be allowed from 14 days before (first) dosing until the end of the trial. No alcoholic or caffeinated drinks, or xanthine-containing products (eg chocolate) will be allowed during the period from 24 h before admission until the end of the period of residence, and for 24 h before each outpatient visit (including screening). Subjects should be advised to avoid eating food containing poppy seeds

from screening until the end of the study, because that can cause a positive drugs of abuse test result.

No strenuous exercise will be allowed from 24 h before admission, and for 48 h before each outpatient visit (including screening).

Regular smokers or users of tobacco and/or nicotine containing products (including e-cigarettes) are excluded from the study (see section 9.3). ‘Social’ smokers or vapers must abstain from smoking/vaping from 1 month before their first dose of study medicine until the end of the study.

Subjects must not sunbathe or use a sunbed during the study.

Subjects must use a reliable method of contraception, as follows.

Men

Male subjects must not plan to father a child, or donate sperm, during the trial (from [first] dose until their follow-up visit).

During the trial (from [first] dose until their follow-up visit), male subjects must not have sex without using a condom, if their partner is a woman of childbearing potential.

Women

Women of childbearing potential must use a low user dependent method of contraception during the trial. They must have been using that method for at least 28 days before the start of the trial. Low user dependent methods of contraception include:

- intrauterine device (IUD)
- intrauterine hormone-releasing system (IUS)
- bilateral tubal occlusion
- vasectomised partner (with surgical success confirmed by medical assessment)

A woman is considered to be of non-childbearing potential if she meets one of the following criteria:

- is post-menopausal (the last menstrual period was at least 12 months ago, and follicle-stimulating hormone (FSH) at screening confirms post-menopausal status)
- has no uterus, ovaries or fallopian tubes

Women who are taking hormone replacement therapy (HRT) must use contraception (as described above) during the trial.

Subjects who practise true abstinence or who only have same-sex relationships need not use contraception, provided it is in line with their preferred and usual lifestyle (note: periodic abstinence (eg calendar, ovulation, symptothermal, and post-ovulation methods) and withdrawal are not acceptable methods of

contraception). Should any such subject stop practising true abstinence, they must use contraception as described above.

12 Procedures and observations

Only subjects who meet all the inclusion and no exclusion criteria will be eligible for enrolment into the trial (see section 9). Each subject will be allocated a unique trial number (see section 10.5).

The schedule of procedures is in section 12.1.

Additional timepoints may be introduced, and changes to timepoints may be made, in accordance with section 12.2.

The following assessments will be made.

Safety and tolerability:

Laboratory assessments (routine haematology, clinical chemistry, and urinalysis), physical examinations, 12-lead ECGs, and vital signs (blood pressure, pulse rate, respiratory rate, and tympanic temperature) and C-SSRS (Part C only) will be done frequently until the subject's last visit. Cardiac telemetry (Part A only) will be done from 1 h before until 24 h after dosing. AEs will be recorded from screening until the subject's last visit.

Laboratory safety variables to be assessed during the study are in Table 11.

From screening until the follow-up visit, AEs and concomitant medication will be documented as they are reported by the subjects. Subjects will be questioned (using a non-leading question, such as 'How are you feeling?') about AEs on admission to the ward, when procedures are done, and when they return to the ward at follow-up.

As previous safety studies in animals (28-day toxicity study in dogs) indicated that BEN8744 may cause sedation, an OAAS/S and VAS will be used to monitor alertness and sedation. The OAAS/S and VAS will be done immediately before PK blood samples frequently up to 72 h after dosing in Parts A and B, and up to 72 h after dosing on Day 1 in Part C.

Pharmacokinetics

Blood samples for assay of BEN8744 will be taken before, and frequently up to 72 h after dosing in Parts A and B, and up to 72 h after dosing on Day 1 and Day 14 in Part C.

Urine will be collected continuously for up to 72 h after dosing in Part B, and may be taken for up to 72 h after dosing on Days 1 and 14 in Part C, for assay of BEN8744 and its metabolites.

A predose faecal sample will be collected from Day -2 to predose on Day 1 in Part B Session 1. Faecal samples will be collected continuously for up to 72 h after dosing in Part B for the exploratory characterisation of BEN8744 and its metabolites.

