After single doses of 2–60 mg, BEN8744 demonstrated a shorter than expected elimination half-life, ranging approximately 2–4 h. At the highest dose tested (60 mg), mean C_{avg} was below IC_{90} . However, a single subject had a higher AUC_{inf} , approximately 2-fold above the mean and above IC_{90} . In all subjects after 60 mg BEN8744, plasma concentrations decreased below the IC_{50} by 11 h postdose. Considering the observed short half-life, and predicted required time above IC_{50} for efficacy in patients, a twice daily dosage regimen will be required in Part C (MAD Phase) to achieve exposures above IC_{50} for up to 18–24 h.

The impact of gut P-glycoprotein (P-gp) efflux and gut cytochrome p450 3A4 (CYP3A4) mediated metabolism was not expected to be significant in humans; however, emerging clinical data suggests there is an impact which is significant at lower doses. Between 2 and 6 mg QD the increase in PK parameters appeared dose-proportional, but escalation between 6, 20 and 60 mg QD resulted in a greater than proportional increase in AUC_{inf} , suggestive of non-linear PK. Additionally, between-subject variation was high. While the linear approach overpredicted exposures at low doses, the mean C_{max} and AUC_{inf} at 60 mg aligns with predicted exposures. Mean apparent clearance (CL/F) decreased with an increase in dose from 6 to 60 mg QD, which may indicate approaching saturation of gut P-gp and CYP3A4. Hence, at higher doses exposure is expected to be closer to dose-proportional.

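### In Part B, section 11 restricts water around dosing in the fasted sessions but not in the fed sessions, so water intake near the dose may differ along with the meal

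*Combined protocol and SAP*

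**What the plan says.** Section 11 (Dietary and lifestyle restrictions) describes each Part B session separately.

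- **Fasted session, B1 and B2.** The fast, with water allowed, runs "overnight for at least 10 h before dosing, until 4 h afterwards". The same sentence adds the water rule: "until 4 h afterwards, and water will not be allowed for 1 h before and after dosing".
- **Fed session, B1.** "Subjects will fast (no food or drink other than water) overnight and will start the breakfast approximately 30 min before dosing". The meal has to be finished no later than 10 min ahead of the dose. The high-fat meal is itemised and includes its drink: "4 ounces of hash brown potatoes, and a glass of whole milk".
- **Fed session, B2.** The dose follows a high-fat or a standard breakfast after an overnight fast. No number of hours and no water rule are given.
- **Both sessions, B1 and B2.** Standard meals and drinks come at 4, 10 and 24 h after dosing, with the same content in each session.

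Section 10.1 gives about 240 mL of water with every treatment. Section 8.1.2 attaches the 10 h minimum to the fasted session only.

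For Part C, section 11 describes a fed morning option that ends: "2 portions of butter/margarine, and 1 portion of jam. Water will not be allowed for 1 h before and after dosing". Twice-daily evening doses, taken about 1 h after dinner, carry the same rule: "Water will not be allowed for 1 h before and after dosing".

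**The concern.** The effect of food on the PK profile is the primary objective of Part B (section 7.1.1). Each group has 6 subjects, each serving as their own control. Section 16.2.7 concludes a food effect if the 90% CI for the fed:fasted ratio of AUCinf, AUClast or Cmax is not contained in 80–125%. The ratio can be read as the effect of the meal only if the meal is what differs between the two sessions.

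As written, a subject in the fasted session may take no water other than the dosing water from 1 h before to 1 h after the dose. The same subject in the fed session may drink during that time. Any influence of that water on exposure would be included in the fed:fasted ratio and attributed to food. The result also helps decide whether Part C is dosed fed or fasted (sections 8.1.3 and 8.5.4).

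**Working it through.** The documents give no figure on this point, so there is nothing to reproduce. The check is a comparison of text, followed by what it implies for the contrast.

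**Step 1. Conditions in the Part B sessions (sections 10.1 and 11).**

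| Condition | Fasted, B1 and B2 | Fed, B1 | Fed, B2 | Matched? |
|---|---|---|---|---|
| Fast before dose or meal | Overnight, at least 10 h | Overnight, no hours given | Overnight, no hours given | Partly: the minimum is missing |
| Water for 1 h before dosing | Not allowed | Allowed during the fast, no cut-off | Not addressed | No |
| Water for 1 h after dosing | Not allowed | Not addressed | Not addressed | No |
| Water with the dose | About 240 mL | About 240 mL | About 240 mL | Yes |
| Stated fast after dosing | Until 4 h | Not stated | Not stated | Wording differs |
| First meal after dosing | 4 h, same content | 4 h, same content | 4 h, same content | Yes |

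The meal schedule largely aligns food after dosing, and an overnight fast precedes both sessions. The condition left open is additional water over 60 + 60 = 120 min around the dose. In the B1 fed session, breakfast occupies roughly 30 to 10 min before dosing, and its drink is specified.

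**Step 2. Does the fed state explain the missing rule?** Section 11 describes eight dosing conditions:

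- With the 1 h water rule (six): Part A; B1 fasted; B2 fasted; Part C fasted morning; Part C fed morning; Part C evening after dinner.
- Without it (two): B1 fed; B2 fed.

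Two of the six conditions with the rule follow a meal, so being fed does not account for its absence. No reason is given. This looks like an omission.

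**Step 3. What it does to the comparison.** On the log scale, write subject i's fed-minus-fasted difference as

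d_i = m + w_i + period effect + error,

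where m is the effect of the meal and w_i the effect of any additional water taken near the fed dose. The 3:3 allocation to sequence (Table 7) balances the period effect. It does not remove w_i, because the laxer water rule belongs to the fed session in both sequences. Averaged over sequences, the estimate is m + mean(w). The model in section 16.2.7 has no term that could separate the two, and the Part B schedule (section 12.1.2) lists no record of fluid intake from which to adjust later.

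**Step 4. Size.** The documents give no volume of additional water and no relation between water intake and BEN8744 exposure. If nobody drinks extra water, mean(w) is 0. Otherwise neither its sign nor its size can be derived.

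**The case against.** The strongest reply is that most of the conditions are already aligned. Both sessions follow an overnight fast. The first meal after dosing is at 4 h with the same content, the dosing water is the same, and the milk is part of the test meal. Subjects are resident on the ward under house rules, with supervised dosing. The text permits extra water in the fed session but does not require it. Section 11 also leaves Part B fasting requirements to the Safety Review Group.

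Much of this stands. A reader might infer that the fed session has no controls or that fluid is unregulated; the points above rule that out. The remaining gap is not closed, however. The Safety Review Group may change the conditions, but the group descriptions are the written default. The content of the house rules is not given, and section 11 states the water rule explicitly for six other conditions. Fixing the dosing water does not limit what is drunk before or after it.

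A reader might also infer that the effect is large for this drug, because section 6.2.4 says of gut P-gp efflux and CYP3A4 metabolism that "emerging clinical data suggests there is an impact which is significant at lower doses". The documents do not support that step. The statement is tentative, the non-linearity is seen across cohorts of different subjects with high between-subject variation, and exposure is expected to be closer to dose-proportional at higher doses. Nothing links exposure to water volume, so dilution figures built on the dose exponents would rest on an assumed mechanism and volume.

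Finally, the mismatch between the Part B and Part C fed conditions is a weak argument for B1, since a high-fat and a standard breakfast differ by design. It has some force for B2 if the standard breakfast is chosen, because the meal described there is the same as in Part C.

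**Conclusion.** The point holds in a limited form. Section 11 states the water restriction, the minimum fast and the explicit post-dose fast for the Part B fasted sessions only. The difference of substance is additional water within 1 h either side of dosing; the other two are mainly wording to align. Because the water rule differs with treatment, any effect it has is inseparable from the meal in Part B's primary comparison.

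A reader might conclude that the fed:fasted ratio is biased. The documents do not show this: extra water is permitted, its uptake is unknown, and the size and direction of any effect cannot be derived. The conclusion assumes only that section 11 is followed as written and that the Safety Review Group or the house rules do not supply a matching rule elsewhere. It is worth correcting because the comparison is the purpose of Part B and the correction is nearly free.

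**What to change.** Reconcile the session descriptions in section 11 so that, for B1 and B2, the fed and fasted sessions state the same:

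- restriction on water before and after dosing, apart from the dosing water and the drink in the test meal;
- minimum fast, counted to the start of the meal in the fed session;
- fast after dosing.

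The meal is then the only planned difference. Align the fasting wording in section 8.1.2 with it. If a difference is intended, say so and give the reason.

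The cost is a sentence or two of text. No procedure, subject or visit is added.
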